Subjects. After obtaining their written informed consent (ages 18-25) or assent (ages 6-17; plus parental consent), children and young adults aged 6-25 years with a diagnosis of ADPKD, based on the presence of bilateral renal cysts when there is a positive family history⁵¹, and normal renal function with an estimated glomerular filtration rate (eGFR) >80 mL/min/1.73 m² (using CKid Schwartz bedside equation for ages 6-17⁵² and the CKD-EPI equation for ages 18-25⁵³) will serve as subjects. Patients will undergo screening and vascular testing at the University of Colorado Denver Division of Renal Diseases and Hypertension Clinical Vascular Physiology Laboratory, which is part of the Clinical Research Unit. A local contracted laboratory (Quest) and medical records will be used for screening for out of state participants. The University of Colorado Denver ADPKD Center has successfully employed this approach in previous and ongoing ADPKD clinical studies^{54,55}, including a recently completed trial by the co-mentor ([name]) in 110 children and young adults with ADPKD⁵⁶. Laboratory analysis will be performed at the University of Colorado Hospital or by Quest, and mass spectrometry analyses will be performed in the iC42 Clinical Research & Development Center. Renal magnetic resonance imaging (MRI) scans will be performed at the Brain Imaging Center. Major inclusion/exclusion criteria are presented in the table below (Table 1). Those who drop-out/do not complete the study will be encouraged to undergo an end-of study visit which will include identical measurements to the ones planned for session 5.

Table 1 Inclusion Criteria	Exclusion Criteria

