In state subjects will come to the Clinical Vascular Physiology Laboratory (sessions 1, 2, 4, 5, and 6) or the Brain Imaging Center (sessions 3 & 7) on 7 separate occasions. Out of state participants (approximately half) will travel twice to Colorado. Sessions 2 & 3 and then 6 & 7 will occur on consecutive days during the same trip (**for a total of 2 out of state trips during the study**). Session 1 (and subsequent safety labs) will be arranged at a local contracted laboratory (Quest) for out of state participants.

- **Session 1:** Screening measurements
- **Session 2:** Baseline measurements
 - Vital signs
 - Blood sampling for measurement of circulating curcumin levels, serum creatinine, ALT and AST and urine sampling for markers of oxidative stress (**all subjects**); blood sampling for markers of inflammation (**subset of subjects 18-25 years**)
 - FMD_{BA} (EDD) and aPWV (arterial stiffness) (**all subjects**), with and without acute inhibition of oxidative stress via systemic i.v. infusion of ascorbic acid (**subset of subjects 18-25 years**)
 - Endothelium-independent dilation to sublingual nitroglycerin (**subset of subjects 18-25 years**)
- **Session 3:** Baseline measurements
 - Abdominal MRI for subsequent analysis of TKV (**all subjects**)
 - Begin study treatment (curcumin or placebo)
- **Session 4:** Safety lab check
- **Session 5:** Mid-study measurement of FMD_{BA} and aPWV for **local (in state) patients only**; safety lab check (all patients)
- **Sessions 6 & 7 (month 12):** Identical to Sessions 2 & 3 (note: subjects will not take a dose the a.m. prior to testing session to avoid any acute effects)

Curcumin. Curcumin will be delivered as a dose of 25 mg/kg/day rounded to the nearest 100 mg, delivered as powder measured in 100 mg and 500 mg scoops (Longvida™, Verdure Sciences). The placebo will contain inert substances (soy lecithin, stearic acid, ascorbyl palmitate, carrot extract) of similar proportions and amounts as in the active powder. The powder delivery will improve adherence, particularly among young children who may have difficulty swallowing capsules. The powder will be delivered mixed with a choice of pudding yogurt, or other foods of similar consistency. Absorption of Longvida™ is the same when taken with a small amount of food compared with water or milk.

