- Tend to ↓ the progression of TKV (adjusted for height), which can be examined further in a longer-duration, larger sample size, future R01 grant

Power Calculations and Statistical Analysis. Power calculations are based on clinically meaningful differences in the primary outcomes (FMD_{BA} and aPWV), limited published literature using curcumin in a healthy older population⁴⁴, and experience of the applicant regarding the variability of the proposed outcomes^{68,69,79}. A sample size of 27 in each group will have 90% power to detect a mean increase in FMD_{BA} of 1.5%, given a standard deviation of 2.0⁶⁸, with $\alpha = 0.025$, adjusted for two primary endpoints. Akazawa et al.⁴⁴ demonstrated in healthy post-menopausal women a ΔFMD_{BA} of +1.5% with curcumin compared to a decrease in FMD_{BA} of -0.2% in controls. Similarly, a sample size of 27/group will have 90% power to detect a mean decrease of aPWV of 100 cm/sec given a standard deviation of 125⁶⁹ with $\alpha = 0.025$, adjusted for two primary endpoints. To account for a potential dropout of 20%, 34 subjects/group will be enrolled.

A sub-sample size of 10 in each group (of 18-25 year olds) will have 89% power to detect a 50% reduction in ΔFMD_{BA} with ascorbic acid (given $\Delta FMD = +3.0 \pm 1.0\%$ with ascorbic acid in the placebo group⁶⁸), with a two-sided $\alpha = 0.05$. Aim 3 will be considered exploratory, thus power was not calculated.

Differences between groups at baseline will be assessed by an independent t-test, and a linear mixed-effects model will be fit to compare curcumin vs. placebo (independent variable) with respect to change in outcomes at 6 and 12 months (dependent variables), with covariates and potential confounders (including puberty) incorporated into the model. This approach will account for the use of multiple time points and is flexible to missing (at random) data. Although I do not expect different responses based on sex or race/ethnicity, and the study is not powered to assess these factors, stratified analysis will be performed and any trends will be noted and studied in a larger follow-up study. Dropouts will be handled using an intent-to-treat analysis.

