b) Data Safety Monitoring Plan. A data safety monitoring board (DSMB) including clinicians (a nephrologist and pediatrician) and a statistician (independent of the study investigators but part of the faculty at the University of Colorado, School of Medicine) will be formed to assess potential adverse events. These data will be prepared by the DSMB statistician, ensuring the study statistician remains blinded until the final analysis. The DSMB will meet annually to review the protocol and will follow the guidelines established by the NIH National Center for Research Resources which include: a) monitoring the progress of the protocol (e.g., reviewing subject recruitment, attrition and minority involvement) and the safety of research participants (e.g., reviewing unblinded data for safety); b) assuring compliance with requirements regarding the reporting of adverse events; c) assuring that any action that results in the temporary or permanent suspension of the protocol is reported to all the appropriate monitoring bodies (i.e., IRB, NIH, FDA, etc.); and d) assuring data accuracy and protocol compliance.

c) Reporting of Side Effects. Subjects will be instructed to report side effects to the investigator and their nephrologist, if not part of the investigative team. Any serious adverse events will be reported to the Colorado Multiple IRB, Verdure Sciences, and the FDA, in accordance with the guidelines of each of these groups. Participants who drop out of the study will be handled using an intent-to-treat analysis.

d) Exit Criteria. The primary exit criteria will include completion of the study, patient request, IRB or DSMB request, or other rationale as determined by the principal investigator or mentors. Other exit criteria are listed below. The number of subjects exiting the study and the reasons for exit will be carefully documented.

Patient Stopping Criteria:

- Withdrawal of informed consent (subject's decision to withdraw for any reason)
- Any clinical adverse event (AE), laboratory abnormality or intercurrent illness which, in the opinion of the investigator, indicates that continued participation in the study is not in the best interest of the subject
- Pregnancy
- Loss of ability to freely provide consent through imprisonment or involuntary incarceration for treatment of either a psychiatric or physical (e.g., infectious disease) illness
- Use of an investigational therapy or device other than study medication

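### Intent-to-treat handling of dropouts is promised but not defined, and a change-score model without baseline leaves out anyone with no post-baseline vascular test

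*Combined protocol and SAP*

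**What the plan says.** Under Power Calculations and Statistical Analysis, a linear mixed-effects model compares curcumin with placebo "with respect to change in outcomes at 6 and 12 months (dependent variables"). Covariates and confounders may be added. Puberty is named; the baseline value of the outcome is not. On incomplete data the section says: "This approach will account for the use of multiple time points and is flexible to missing (at random) data". It ends: "Dropouts will be handled using an intent-to-treat analysis". Human Subjects section 5c (Reporting of Side Effects) repeats this: "Participants who drop out of the study will be handled using an intent-to-treat analysis".

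Three other statements decide what data a dropout can supply:

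- Experimental Design, on visits: "Out of state participants (approximately half) will travel twice to Colorado".
- The same session list, on Session 5: "Mid-study measurement of FMD_{BA} and aPWV for local (in state) patients only". For the out-of-state half, month 12 is therefore the only scheduled vascular test after baseline.
- Subjects, on retrieval: "Those who drop-out/do not complete the study will be encouraged to undergo an end-of study visit", with "identical measurements to the ones planned for session 5".

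No section defines the intent-to-treat set, says whether values from the dropout visit enter the model, or names a sensitivity analysis for data not missing at random.

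**The concern.** Intent-to-treat implies that everyone randomised is analysed as assigned. A model of change scores can use only people who have at least one change score. Someone who leaves before any post-baseline test contributes no row, and the baseline test already in hand goes unused because baseline is neither part of the response nor a named covariate. The tolerance of missing-at-random data helps an in-state dropout who reached month 6. It does nothing for an out-of-state dropout who does not return. For such people the analysis is a complete-case comparison, valid only if dropout is unrelated to baseline as well as to the unseen outcome.

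The second issue is what is being estimated. Where dropouts are not measured again, a missing-at-random model in effect assumes that they would have gone on like those still taking the powder. Reported as intent-to-treat, that could overstate the effect of assignment on both primary endpoints.

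**Working it through.** **Inputs from the plan.** 27 evaluable per group; 20% dropout; 34 enrolled per group, 68 in all; FMD difference 1.5 points with SD 2.0; aPWV difference 100 cm/sec; about half of participants out of state.

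**Assumptions, not in the plan.** Dropout is equally common in and out of state. The timing of dropout, the benefit kept after stopping, the share of dropouts retrieved and the correlation between repeated values are varied or stated below.

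**1. The plan's own figure.** 27 / (1 − 0.20) = 33.75, rounded up to 34 per group. This reproduces. The base of 27 is taken as given here.

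**2. Participants with no row in the model, if none return.** Dropouts: 68 × 0.20 = 13.6. Out of state: 13.6 × 0.5 = 6.8, which is 10% of 68; none of them has an earlier post-baseline test. The other 6.8 are in state and are lost only if they leave before month 6. If a share f does so, the number excluded is 6.8 + 6.8f:

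- f = 0: 6.8
- f = 0.5: 10.2
- f = 1: 13.6

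**3. Effect of assignment against effect had all continued.** Let E be the effect in those who continue, p the dropout rate and r the share of benefit kept after stopping. The effect of assignment is E × [1 − p(1 − r)].

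| p | r | FMD (E = 1.5) | aPWV (E = 100) |
|---|---|---|---|
| 0.1 | 0 | 1.35 | 90 |
| 0.2 | 0 | 1.20 | 80 |
| 0.3 | 0 | 1.05 | 70 |
| 0.2 | 0.5 | 1.35 | 90 |
| 0.2 | 1 | 1.50 | 100 |

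At p = 0.2 and r = 0 the ratio is 1.5 / 1.2 = 1.25. Taking the design difference as E is itself an assumption.

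**4. Effect of retrieval.** The planned change model was simulated for FMD: 1,500 trials, 34 per arm, half local, correlation 0.5 between months 6 and 12, 20% dropout, half of it before month 6, no benefit after stopping. The true effect of assignment is 1.20. The mean estimate was 1.50 with no dropout retrieved, about 1.33 with half retrieved and about 1.19 with all retrieved. The same model thus moves from one target to the other as retrieval rises.

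**5. What leaving out baseline costs.** Treat 2.0 as the SD of change, and let ρ be the correlation between baseline and month 12, assumed 0.3 to 0.7. With equal SD σ at both times, the variance of change is 2σ²(1 − ρ), and after conditioning on baseline the residual variance is σ²(1 − ρ²). The ratio of standard errors is √[(1 + ρ)/2]: 0.806 at ρ = 0.3 and 0.922 at ρ = 0.7, a reduction of about 19% and 8%. Simulation of the month-12 comparison gave about 8–18%.

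For bias, suppose that dropout in one arm shifts the mean baseline of those remaining by δ SDs. The unadjusted change difference is then off by (1 − ρ)σδ in size. Since σ = 2.0/√[2(1 − ρ)], this equals δ√[2(1 − ρ)]. With δ = 0.18, as an illustration, it is 0.21 FMD points at ρ = 0.3 and 0.14 at ρ = 0.7. Simulated baseline-dependent dropout gave the same range of about 0.14–0.21, and conditioning on baseline removed it.

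**The case against.** Several stronger readings are tempting, and the documents do not support them.

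- A reader might infer two conflicting rules. Intent-to-treat says who is analysed and in which arm; a mixed model says how. They can be applied together. The gap is that the first is undefined and the second, as written, does not include everyone.
- A reader might infer that the plan estimates an on-treatment effect. No section excludes values measured after stopping, and dropouts are encouraged to return. With full retrieval the planned model gives the effect of assignment (step 4).
- A reader might quote a 25% overstatement as the expected error. It needs no retrieval and complete loss of benefit together, and the documents give neither.
- A reader might infer that the excluded participants would go unidentified. Human Subjects section 5d requires the number of exits and the reasons to be documented.

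There is also a technical objection to modelling baseline as a response. A participant with only a baseline value informs the common baseline mean, which cancels from the arm difference, so that person adds little to the treatment contrast. This is right. The gain comes from conditioning on baseline for everyone who does have follow-up (step 5). The plan's general allowance for covariates would permit that adjustment, but does not name it.

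The retrieval visit answers the concern only in part. Attendance is encouraged, not assured, and its content is tied to Session 5, which on its wording gives FMD and aPWV to in-state patients only. The dropouts with no earlier test are therefore those whom the visit may not measure.

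**Conclusion.** The point holds in a limited form and should be corrected. Intent-to-treat is named twice and never made operational. The primary model omits randomised participants who have no post-baseline vascular test: about 7 of 68 at the plan's dropout rate if none return, and up to about 14 if in-state dropouts also leave before month 6. It makes no stated use of baseline values, at a cost of roughly 8–19% in standard error, and of possible bias when dropout depends on baseline; both figures rest on assumed correlations.

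The estimate departs from the effect of assignment only to the extent that dropouts go unmeasured and lose benefit. The upper-end scenario is 1.2 against 1.5 FMD points and 80 against 100 cm/sec. With full retrieval or lasting benefit the gap is about zero. Confidence is medium, because the documents do not settle how dropout-visit values will be used.

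**What to change.** 1. Fit baseline, month-6 and month-12 values jointly with a common baseline mean for the two arms, or keep the change model and adjust it for baseline. Define the analysis set as all randomised participants with a Session 2 test, analysed as assigned. State that values measured after stopping powder are included, among them those from the dropout visit.
2. Describe the resulting estimate as resting on missing at random.
3. Pre-specify one sensitivity analysis for FMD and one for aPWV: reference-based multiple imputation, with missing month-12 values of curcumin dropouts imputed from the placebo arm. Report it beside the primary result. It rests on a strong assumption of its own, so it should not be the only basis for an intent-to-treat statement.
4. Reconcile the dropout visit described under Subjects with the Session 5 entry, so that it is clear which vascular tests out-of-state dropouts receive.

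Items 1 to 3 cost SAP wording and one further analysis per primary endpoint, and need no added participants; item 4 is a clarification. The wording should be fixed before unblinding. The downside is that the sensitivity estimate may be smaller than the primary one.

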An increase in **total kidney volume (TKV)** precedes the decline in kidney function, which is typically delayed until the 4th decade of life in patients with ADPKD, and TKV is a prognostic biomarker of future kidney function decline¹⁸. Thus, a decrease in rate of TKV growth, as measured by **magnetic resonance imaging (MRI)** is an important indicator of kidney disease progression early in the course of ADPKD.

Curcumin is a safe, naturally occurring polyphenol found in the Indian spice turmeric that has a unique ability to activate transcription of key antioxidants, suppress inflammation, and reduce proliferation. Curcumin reduces arterial dysfunction in various rodent models of vascular dysfunction^{19,20}, and my preliminary data demonstrate that it also reduces age-associated vascular dysfunction in humans. Importantly, curcumin also slows cyst growth in kidney cells *in vitro*²¹ and *in vivo*²². Thus, curcumin is a promising **nutraceutical** to slow progression of renal and cardiovascular disease in children with ADPKD. However, there is presently **no information available** regarding the potential therapeutic benefits of curcumin to treat arterial dysfunction and slow kidney growth in this population.

Accordingly, the **primary aim** of this application is to determine the efficacy of curcumin for improving FMD_{BA} and reducing aPWV in 68 children/young adults with ADPKD. A key **secondary goal** is to obtain insight into the mechanisms by which curcumin therapy may reduce arterial dysfunction. Last, a **third exploratory aim** is to determine if treatment with curcumin slows kidney growth. These aims will be tested in a double-blind, placebo-controlled, randomized clinical trial conducted in children/young adults aged 6-25 years with ADPKD.

Hypothesis 1: Oral curcumin therapy will reduce vascular endothelial dysfunction (increase EDD) and large elastic artery stiffness in children and young adults with ADPKD as compared to placebo.

Specific Aim 1: To determine **non-invasively**: a) FMD_{BA} and b) aPWV before and after 12 months of oral curcumin (25 mg/kg/day) or placebo; and after 6 months in a sub-set of all local patients.

Hypothesis 2: The improvements in arterial function observed with oral curcumin treatment will be associated with reduced oxidative stress and inflammation.

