- Significant non-compliance with protocol (i.e., procedures, assessments, medication, etc.)
- Serious acute hypersensitivity reactions to investigational drug

Study Stopping Criteria:

The DSMB may recommend study stopping if:

- The data show a significantly increased risk of serious adverse effects in the treatment group.

- It becomes clear that successful completion of the study is not feasible (e.g. there is an excess of patient dropout, missing data, lack of recruitment etc).

Clinical Trials.gov Requirements

The application includes a trial which requires registration at ClinicalTrials.gov. This registration will be performed.

References

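### Treatment-related stopping reasons are written as exits from the study, and apart from one encouraged, undated closing visit the plan provides no follow-up to month 12 after a participant stops the powder

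*Combined protocol and SAP*

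**What the plan says.** Section 5(d), Exit Criteria, gives general reasons for leaving, including a catch-all for reasons set by the principal investigator or mentors. It then lists further exits under Patient Stopping Criteria. Three concern the powder:

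- an adverse event, an intercurrent illness or a laboratory abnormality, if it, "in the opinion of the investigator, indicates that continued participation in the study is not in the best interest of the subject";
- "Significant non-compliance with protocol (i.e., procedures, assessments, medication, etc".);
- "Serious acute hypersensitivity reactions to investigational drug".

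Pregnancy and use of another investigational therapy are also listed. The section adds that "The number of subjects exiting the study and the reasons for exit will be carefully documented".

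Under Approach, Subjects, those who drop out or do not complete "will be encouraged to undergo an end-of study visit which will include identical measurements to the ones planned for session 5". In Experimental Design, session 5 is a safety lab check for everyone, with FMD and aPWV for "local (in state) patients only". About half of the participants are expected to come from out of state.

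Specific Aim 1 sets the primary outcomes "before and after 12 months of oral curcumin (25 mg/kg/day) or placebo; and after 6 months in a sub-set of all local patients". Section 5(c) promises that "Participants who drop out of the study will be handled using an intent-to-treat analysis". Power Calculations and Statistical Analysis repeats this and names a linear mixed-effects model for change at 6 and 12 months, described as tolerating data missing at random.

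Two provisions come before or alongside exit. Intolerable symptoms lead to a dose reduction from 25 to 15 mg/kg/day (Potential Risks, Curcumin). Participants are asked to report side effects, and serious events are reported onward (section 5(c)).

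**The concern.** Stopping the product and leaving the study are different events, and the plan has only one status for both. A participant who cannot tolerate the powder or does not take it leaves the study, and the month-12 visit goes with it. An intent-to-treat comparison needs those outcomes most, because these exits are tied to treatment. The plan itself expects adherence to vary (Duration of Treatment).

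The mixed model does not replace the missing values. Under missing at random it in effect predicts leavers from participants who stayed, most of them still on powder. An out-of-state leaver has no month-6 vascular test, so without vascular testing at the closing visit that person supplies no change value at all.

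There is also a safety side. Participants are as young as 6, and someone removed for a laboratory abnormality has no stated schedule for repeat labs beyond one voluntary visit without a date.

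**Working it through.** **Plan's own figure.** 27 evaluable per group with 20% dropout: 27/0.8 = 33.75, rounded up to 34 per group, 68 in total. This reproduces. The allowance is 34 − 27 = 7 per group, for all causes.

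**Inputs from Power Calculations and Statistical Analysis.** FMD: effect E = 1.5, SD 2.0. aPWV: effect E = 100 cm/sec, SD 125. Evaluable n = 27 per group.

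**Yardstick.** Planned SE = SD × √(2/27).
- FMD: 2.0 × 0.2722 = 0.544
- aPWV: 125 × 0.2722 = 34.0 cm/sec

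**Assumptions, not given in the plan.** k of 34 curcumin participants exit for these reasons and lose all effect; r of the k are measured at a closing visit that is treated as month 12; placebo leavers have no effect to lose.

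**Formulas.**
- Effect in all randomised = E × (34 − k)/34
- Effect estimated from those measured = E × (34 − k)/(34 − k + r)
- Gap = estimated − all randomised

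| k | r | FMD gap | in SE | aPWV gap (cm/sec) | in SE |
|---|---|---|---|---|---|
| 2 | 0 | 1.500 − 1.412 = 0.088 | 0.16 | 5.9 | 0.17 |
| 4 | 0 | 0.176 | 0.32 | 11.8 | 0.35 |
| 7 | 0 | 1.500 − 1.191 = 0.309 | 0.57 | 20.6 | 0.61 |
| 7 | 2 | 1.397 − 1.191 = 0.205 | 0.38 | 93.1 − 79.4 = 13.7 | 0.40 |

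If half the effect persists after stopping, each gap halves (FMD 0.044 to 0.154 with r = 0). If all of it persists, the gap is zero.

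**Safety labs.** The plan gives two schedules. Safety Checks has creatinine, ALT and AST at months 1, 6 and 12; the paragraph on minimizing risks from curcumin administration has months 1, 6 and 9.
- Exit between months 1 and 6: 2 of 3 labs still to come on either schedule.
- Exit between months 6 and 9: 1 of 3 on either schedule.
- Exit between months 9 and 12: 1 of 3 on the first schedule, none on the second.

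The phone checks conflict too: monthly in the first place, months 1, 3, 6 and 9 in the second. Neither place says whether labs or calls continue after exit.

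**The case against.** The adverse-event criterion is softer than it first looks. A reader might infer that any adverse event forces exit. It does not: exit follows only if the investigator judges that being in the study is against the participant's interest, and an event for which stopping powder is enough need not meet that test. For this criterion the defect is silence about stopping powder. The firmer evidence is the non-compliance and hypersensitivity items, and those are limited to significant and serious cases.

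The plan also does more for leavers than nothing. The closing visit is offered to everyone who drops out, with safety labs for all and vascular testing at least for local patients. Nor does the plan say that calls and labs stop at exit; it is silent. These provisions narrow the gap. They do not close it, because the visit is voluntary, has no date, and is not the month-12 measurement.

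Few such exits may occur. The plan expects side effects to be few, mainly gastrointestinal and transient, and dose reduction comes first. Dose-reduced participants and partial adherers who stay still contribute data. This argues for the lower end of the range. Finally, the section on COVID-19 describes participants already due for their end-of-study visit, so a change at this version cannot recover earlier exits. That stands.

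**Conclusion.** The concern holds as a gap in the exit rules. Followed as written, they send some treatment-related stoppers out of the study and leave their month-12 primary outcomes to an optional visit at another time. Safety follow-up after stopping has no stated schedule.

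A reader might go further and infer that the trial's estimate is biased upward. The documents do not support that as a flat statement. The direction depends on curcumin leavers losing benefit and on their values being missing; closing-visit data entered as final values could act differently. The plan gives no exit rate by reason and no expected attendance, so neither the bias nor the gain from the fix can be sized. The figure for 7 of 34 (0.31 FMD points; 20.6 cm/sec) is a ceiling, not an expectation: it assigns the whole all-cause allowance to these exits, including consent withdrawals that no rule change would recover. At 2 of 34 the gap is 0.09 FMD points and 5.9 cm/sec, both under a fifth of the planned standard error.

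This is a worthwhile, inexpensive improvement. It does not invalidate the design.

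**What to change.** In section 5(d), state that medication non-compliance, hypersensitivity, and adverse events or laboratory abnormalities for which stopping powder is enough are reasons to stop powder and not to leave the study. Then:

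- Invite these participants, on a voluntary basis, to the scheduled safety calls and labs, after reconciling the two schedules.
- Invite them to the month-12 visit at its original date, with FMD and aPWV for all, and to month 6 as well if local.
- Record the date and reason for stopping powder.
- Limit the catch-all clause so that stopping powder alone is not a ground for study exit. Leave the other exit criteria as written.
- In pregnancy, stop powder, omit MRI and other contraindicated procedures, and keep safety contact.

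The cost is protocol and consent wording. The calls, labs and visits are already scheduled for every participant, and out-of-state safety labs are done at a local contracted laboratory. The downsides are that some will decline, and that visits, blood draws and one out-of-state trip are incurred for people off powder, including any with a hypersensitivity reaction. A late amendment helps only those still enrolled.
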